The COPD cohort will include all adults aged 35 and over with a recorded diagnosis of COPD at any point before the cohort entry date.⁴¹ This method of identifying COPD has previously been validated in CPRD.⁴¹ Code lists to identify COPD will be reviewed by a clinical expert before use. To be included, patients must also have a record of current or former smoking in CPRD.

As in the asthma cohort, patients who have a record of other chronic respiratory conditions at any point before the cohort entry date will be excluded. People who use a leukotriene receptor antagonist (LTRA) within 3 years of the cohort entry date will be excluded as this indicates asthma, as will people who are prescribed a LABA/LAMA and ICS within 3 months before the cohort entry date, as this indicates severe COPD.

Censoring

For all cohorts, cohort exit will be defined as the first of either occurrence of the outcome (for each analysis), death, disenrollment from GP practice, the last date of data availability, or the end of the COVID-19 wave (31st August 2020 for wave 1, 30th April 2021 for wave 2).

M. Comparator groups

The study will use an active comparator group including all people with recorded asthma within 3 years or COPD at any point before the cohort entry date (1st March 2020 or 1st September 2020, respectively) who received a prescription for inhaled medication for asthma or COPD, but no ICS prescription.

The comparator group for the asthma cohort will be people who were not prescribed medication containing ICS and were prescribed a non-ICS inhaled medication for asthma. For the COPD cohort, the comparator group will include people who were not prescribed a medication containing ICS and were prescribed a LABA/LAMA separately or in combination for COPD. Exposures and exposure durations in the comparator group will be calculated in the same way as in the ICS-exposed group.

N. Exposures, outcomes and covariates

Exposure

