before the previous one is estimated to have been completely used, we will assume stockpiling occurred and assign the maximum total days of exposure possible with the combined prescriptions. Patients who switch treatment groups will be considered exposed to the active comparator/ICS group from the date of the switch, and those who discontinue treatment or switch to a treatment not under study will be censored at discontinuation or switch.

Patients will be considered exposed from the date the prescription was issued, as ICS have been shown to exert anti-inflammatory effects within hours of administration.⁴³

Outcomes

- SARS-CoV-2 infection, defined as a recorded positive test for SARS-CoV-2 in the primary care record sourced from the Second Generation Surveillance System (SGSS).
- hospitalisation with COVID-19, defined as admission to hospital with an ICD-10 code for COVID-19, ascertained using HES data.
- death with COVID-19, defined as death with an ICD-10 code for COVID-19 listed as an underlying or contributing cause of death in the ONS death registry.

Covariates

- demographic and lifestyle variables at baseline: age, sex, body mass index (BMI), smoking status, ethnicity, socioeconomic status (Index of Multiple Deprivation, IMD)
- ever-present comorbidities at baseline: chronic kidney disease, hypertension, heart failure, other heart diseases, diabetes, cancer, immunosuppression
- time-updated covariates: influenza vaccination within one year before the cohort entry date, pneumococcal vaccination within 5 years before the cohort entry date, vaccination against COVID-19 (wave 2 only)
- calendar time, COVID-19 prevalence figures (ONS)
- asthma cohort only: number of recorded asthma exacerbations (emergency department visit, hospitalisation or prescription of an oral corticosteroid for asthma⁴⁴) within 1 year before the cohort entry date
- COPD cohort only: number of recorded COPD exacerbations (defined using a validated algorithm⁴⁵) within 1 year before the cohort entry date.

O. Data analysis

Descriptive study:

Population-level measures of ICS use that will be determined per calendar month are:

- Number and proportion of incident and prevalent users over the course of follow-up for each calendar month:
 - Prevalent ICS exposure will include people with an ICS prescription recorded on any day during that month.

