- Incident ICS exposure will be defined as a new ICS prescription with no prescription in the previous 6 months. Prevalent users will therefore also include incident users.
- The denominator will be all people with asthma or COPD in each month **Error!**

Reference source not found..

- Number of individual prescriptions per person per month (absolute number).
- Dosages prescribed: median or mean daily dose among those prescribed ICS for any given month.
- Discontinuation of ICS or date of treatment switch: number and proportion of people who have ≥ 6 months of no ICS-containing inhaler prescription.

This study will be descriptive. Results will be presented as absolute numbers and proportions as bar graphs.

The results from this study will inform the exposure definition that will be used in the comparative cohort study (see section on Exposure definitions). This study will be completed before starting the analyses for the subsequent comparative cohort studies.

Comparative cohort studies:

We will conduct descriptive analyses (frequency, percentages, mean [SD] and median [IQR]) to assess characteristics of the patients in each cohort, stratified by exposure group at baseline. Categorical variables will be compared using χ^2 tests. Continuous variables will be compared using t-tests for normally distributed variables and Mann-Whitney test for non-normally distributed variables. Time to each outcome will be presented using Kaplan-Meier plots using time in study as the time scale.

Propensity scores will be generated using logistic regression to estimate likelihood of ICS prescription based on baseline characteristics. All pre-specified covariates will be included in the logistic regression.

The association between ICS prescription and each outcome will be estimated using a Cox regression model to calculate hazard ratios and 95% CIs, using time in study as the time scale. Univariable models, models adjusted for age and sex, and propensity score weighted models will be presented. Schoenfeld residuals will be used to graphically assess the validity of the proportional hazards assumption. If the proportional hazards assumption is violated, we will use interaction terms between the exposure and time to describe any variations in the hazard ratio over time.

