The distribution of confounders will be compared descriptively between users and non-users of ICS. We will use multivariable regression, and propensity scores where appropriate, to adjust for confounding. Covariates used to estimate the propensity score will be selected based on literature and are listed in section N. If a time-updated exposure definition is used, we will generate time-updated confounders.

We will use quantitative bias analysis to quantify the extent to which unmeasured confounding could bias our studies.

R. Missing data

We expect some missing covariate information for BMI, smoking status, and ethnicity. Missing data on ethnicity will be supplemented using HES data.⁵⁷ The characteristics of individuals with and without missing data will be compared to identify systematic differences which may bias the results. The primary analysis will be conducted excluding variables with a considerable number of missing values (>10%). We will consider using multiple imputation or complete records analysis for variables that may be important confounders, depending on the degree of missingness.

S. Patient and user group involvement

We are exploring ways to obtain patient input to contextualise the experiences of people with asthma or COPD during the pandemic, in particular how they may have used or stockpiled prescriptions of ICS in waves 1 and 2.

T. Limitations

An aim of this project is to address some of the limitations of observational research using QBA. Many of the limitations that may affect this study of ICS and COVID-19 outcomes, such as incomplete ascertainment of SARS-CoV-2 infections, unmeasured confounding, and collider bias, will be addressed using QBA. The source and uncertainty about the bias parameters may not always be known and will likely involve a combination of extrapolation from published literature, estimates from other studies, and detailed discussion with a respiratory clinician. For this reason, we will explore a range of values for each bias parameter.

The data source has some missing covariate information. We will exclude covariates with large amounts of missing values from the primary analysis and will consider conducting a sensitivity analysis including those variables using multiple imputation or complete records analysis, depending on the degree of missingness. Furthermore, quantitative bias analysis will be used to assess the extent to which unmeasured confounders may impact study results.

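### The 10% missingness rule conflicts with the rule that all listed covariates enter the propensity score, and could drop BMI, ethnicity or (asthma only) smoking from the primary analysis

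*Protocol*

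**What the plan says.** Two sets of statements govern which covariates the primary model holds.

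**Inclusion.** Section O (comparative cohort studies) says of the propensity score: "All pre-specified covariates will be included in the logistic regression". Section Q adds: "Covariates used to estimate the propensity score will be selected based on literature and are listed in section N". Section N's first covariate group reads: "demographic and lifestyle variables at baseline: age, sex, body mass index (BMI), smoking status, ethnicity, socioeconomic status (Index of Multiple Deprivation, IMD").

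**Exclusion.** Section R opens with "We expect some missing covariate information for BMI, smoking status, and ethnicity" and then sets the rule: "The primary analysis will be conducted excluding variables with a considerable number of missing values (>10" (that is, above 10%). Section T restates it without the number: "We will exclude covariates with large amounts of missing values from the primary analysis".

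Three further statements bear on how far the exclusion reaches:

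- On ethnicity, section R says: "Missing data on ethnicity will be supplemented using HES data".
- On the COPD cohort, section L says: "To be included, patients must also have a record of current or former smoking in CPRD".
- For possibly important confounders, section R says the team will consider multiple imputation or complete-records analysis. Section T describes this as a possible sensitivity analysis.

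**The concern.** The propensity score decides what the primary comparison is adjusted for. Among the models section O lists for presentation, only the propensity-score-weighted one goes beyond age and sex, so a covariate left out of the score drops out of the main adjustment. As written, one analyst could keep BMI under section O, another could drop it under section R, and both would be following the protocol.

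The exclusion rule is also a weak one on its merits. It selects confounders by completeness, not by importance, so a measured and pre-specified confounder can become an unmeasured one. The study sets out to separate bias from effect, and its bias analyses start from these estimates. Confounding that could have been removed with data already held would carry through to the bias-adjusted results.

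**Working it through.** The protocol has no figure on this point to reproduce: it gives no missingness percentage for any variable. The check is therefore textual, with an illustration of size on assumed inputs.

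**1. Do the rules conflict?** Section O admits every pre-specified covariate and makes no exception for missing data. Section Q identifies those covariates as the section N list. Section R removes any variable above 10% missing from the primary analysis, and section T repeats the removal. For a section N covariate that is, say, 12% missing, O and Q require it in the score and R and T require it out. Neither side refers to the other.

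**2. Which covariates can the rule reach?**

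- BMI: either cohort. No supplementary source or entry criterion protects it.
- Ethnicity: either cohort, but less likely. HES fills gaps, and section L requires eligibility for HES linkage. Residual missingness is not stated.
- Smoking status: asthma cohort only. In COPD a record of current or former smoking is required for entry, so it cannot fail on missingness.

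**3. What happens to a dropped covariate?** Imputation and complete-records analysis are only to be considered. Section T and the bias-analysis objective in section D cover unmeasured confounders in general. The confounding part of section P, however, gives parameters only for severity of respiratory disease. No bias-analysis parameters are specified for BMI, smoking or ethnicity.

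**4. How large could the bias be?** For an omitted binary confounder with prevalence p1 in ICS users and p0 in comparators, and outcome ratio R, the hazard ratio is multiplied by

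F = [1 + p1(R − 1)] / [1 + p0(R − 1)].

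Every p1, p0 and R below is assumed; none comes from the protocol.

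- Obesity, 40% v 33%, R = 1.5: F = 1.200 / 1.165 = 1.030, ln F = 0.030.
- Minority ethnicity, 12% v 18%, R = 1.8: F = 1.096 / 1.144 = 0.958, ln F = −0.043.
- Both dropped, treated as independent: 1.030 × 0.958 = 0.987.

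Wider range:

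- 40% v 25%, R = 2.5: F = 1.600 / 1.375 = 1.164.
- 25% v 35%, R = 2.5: F = 1.375 / 1.525 = 0.902.
- 30% v 25%, R = 1.2: F = 1.060 / 1.050 = 1.010.

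**5. Against what benchmark?** Section K says the study is powered for hazard ratios of 1.1 or higher for a positive test in asthma, and above 1.4 (asthma) and 1.7 (COPD) for death. The single-variable shifts compare as follows:

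- ln 1.1 = 0.095: 0.030 / 0.095 = 31% (obesity) and 0.043 / 0.095 = 45% (ethnicity).
- ln 1.4 = 0.336: 9% and 13%.
- ln 1.7 = 0.531: 6% and 8%.

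**The case against.** The best defence is that the two rules can be read together. Section O states the general model, with no data-driven selection, and section R is the specific missing-data exception, which section T confirms. That reading is reasonable, but the protocol does not state it. Even if it were adopted, a completeness cut-off would still decide which confounders are adjusted for. Section R does recognise that some of these variables may be important confounders, and it does not itself confine imputation to sensitivity analysis; only section T does. It still makes no commitment.

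A reader might infer several stronger things that the documents do not support:

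- *That the rule will remove BMI, smoking and ethnicity.* Section R expects only some missing data and gives no rates. HES may keep ethnicity below 10%, and smoking cannot be lost this way in COPD.
- *That the bias analysis cannot help.* Section T invokes it for unmeasured confounders generally, right after the exclusion, and section P calls severity a likely key source, not the only one. Coverage of a dropped covariate is unclear; it is not ruled out.
- *That the adjustment set will differ across the four cohorts.* The text does not say in which population the 10% is assessed. This is possible, not established.
- *That the bias is known to be material.* The inputs are assumed and the two worked shifts run in opposite directions. Retained correlates such as deprivation, diabetes and hypertension may absorb part of either.

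These points limit the claim about size. They do not resolve the conflict or justify the cut-off.

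**Conclusion.** The point holds in conditional form. Sections R and T conflict with sections O and Q over which covariates enter the primary model, and no text gives precedence. That follows from the wording alone and rests on no assumption.

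The consequence depends on missingness that the protocol does not report. If it exceeds 10%, section R as written takes a measured confounder out of the primary estimates, with no firm commitment to adjust for it elsewhere.

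The size cannot be derived from the documents. Single-variable shifts of about 3 to 4% either way, or factors of about 0.90 to 1.16 under wider assumptions, are illustrations. They assume a binary confounder, no adjustment through correlated covariates, and R acting as a risk ratio. Shifts of 3 to 4% are modest beside the detectable hazard ratios for death. They are not negligible beside the 1.1 quoted for a positive test in asthma, and the extremes of the wider range reach or exceed that effect.

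**What to change.** Reconcile sections O, Q, R and T before any outcome model is fitted.

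- Keep all section N covariates in the primary propensity-score model.
- Multiply impute the incomplete covariates within each of the four cohorts, with exposure and outcome in the imputation model.
- Move the model that excludes covariates above 10% missing, and the complete-records analysis, to sensitivity analyses. Commit to running them.
- If the authors prefer to keep the exclusion as primary, the minimum is to state in section O that section R overrides it, to name the population in which the 10% is assessed, and to give bias-analysis parameters for any covariate dropped. That settles the conflict but leaves the avoidable confounding in place.

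The cost is wording in four sections and computing time. The main price is reliance on missing-at-random, which the protocol does not establish for these variables. The two sensitivity analyses would show how much the result depends on it.
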